### 934 **7.2.1.2 Glucose Level Triggering a Counterregulatory Response**

936 For each hormone, the glucose level at which a counterregulatory response was observed will be  
937 treated as a secondary outcome. A response will be defined as the first glucose level at which there  
938 was a sustained increase of the hormone concentration at least 3 standard deviations above baseline.  
939 If no such increase is observed, then the subject will be deemed not to have responded to  
940 hypoglycemia.

941  
942 If the outcome values are not skewed a regression model with a normal distribution and interval  
943 censoring will be fit to the data using maximum likelihood. Age group and the baseline hormone  
944 value will be included as independent variables. If significant non-linearity is detected with the  
945 baseline hormone, it will be divided into categories and treated as a discrete variable. If the values  
946 show a skewed distribution then an alternate distribution such as a Weibull or lognormal will be fit  
947 by maximum likelihood. If no distribution can be found to give a good fit to the data, then a semi-  
948 parametric proportional hazards regression will be fit.

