## 272 **1.2 Study Objectives**

273 The primary objective of this study will be to compare the glucose level at which counter-regulatory  
274 hormone responses occur during hypoglycemia in young children with diabetes, with the glucose  
275 level counter regulatory hormone responses that occur in older children with diabetes. We  
276 hypothesize that the children in the younger age group will not have a counterregulatory response  
277 until a lower glucose level is reached compared with children in the older age group.

278  
279 Secondary objectives will be:

- 280  
281 1 To assess signs and symptoms at different glucose levels of hypoglycemia in younger children  
282 and compare those with the older children. Furthermore, symptoms will be compared to counter  
283 regulatory hormone levels in the two age groups. Symptoms will be assessed using physiologic  
284 data and using an age-appropriate questionnaire that would be completed during the test by the  
285 subject (where appropriate) and by a parent.
- 286  
287 2 To assess whether there is a difference in counter-regulatory hormone response in each age  
288 group, among those who had at least 2-3 episodes of hypoglycemia per day or night prior to the  
289 study compared with those who had an occasional or no episodes of hypoglycemia prior to the  
290 test. Subjects will wear a Guardian RT for 6 days ( $\pm 1$  day) prior to the test to assess episodes of  
291 hypoglycemia.
- 292  
293 3 To examine the accuracy of the Guardian-RT during hypoglycemia in children with type 1  
294 diabetes.

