### 524 **3.3.2 Blood Samples for Hormone Concentrations**

526 Blood samples will be collected for epinephrine, norepinephrine, cortisol, glucagon and GH at  
527 baseline when the subject's glucose level is between 95 and 110 mg/dL (in duplicate) and when the  
528 glucose levels are <90, <80, <70, and <60 mg/dL. A final sample will be collected 15 minutes  
529 following the treatment with intravenous glucose when the subjects glucose level is <60 mg/dL.

530  
531 As permitted by weight, additional samples may be collected for possible later analysis of  
532 pancreatic polypeptides, IGF BP1, insulin and others each time a sample is collected for glucose  
533 and hormone concentrations.

534  
535 All samples collected for hormones will be collected, frozen, and shipped to the central laboratory  
536 for storage. A determination will be made once the primary outcome is known regarding which  
537 samples to process.

538

539 **3.4 Post-Subcutaneous Insulin Infusion Test**

540 Once the study endpoint is reached (the first time the glucose is <60 mg/dL using the study HGM),  
541 the basal rate will be returned to normal and the subjects will be treated with intravenous glucose.  
542 An additional blood sample will be collected for laboratory determination of glucose and hormone  
543 concentrations 15 minutes following the treatment with intravenous glucose. Subjects will then be  
544 given breakfast and discharged. Prior to discharge, the sensor(s) will be removed and downloaded.  
545 The subject's insulin pump will be downloaded if possible.

546

547 **3.5 Daily Activities**

548 Subjects will be permitted to perform their usual indoor activities during the hospitalization, except  
549 during the subcutaneous insulin infusion test where they will be restricted to bed.

550

551 **3.6 Diet**

552 The prescribed diet will be at the discretion of the investigator.

553 **CHAPTER 4**  
554 **EVALUATION OF CONTINUOUS GLUCOSE MONITORS**  
555

556 **4.1 Overview**

557 The accuracy of the Guardian-RT will be evaluated during the inpatient phase.  
558

559 **4.2 Inpatient Accuracy Evaluation**

560 The inpatient stay is described in the prior chapter.  
561

562 At the start of the admission, the following will be done:

- 563 • Areas where a Guardian RT sensor was worn during the previous week will be assessed for  
564 skin reactions.
- 565 • Subjects will continue using the Guardian RT sensor inserted prior to the admission.

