### 7.2 Analysis Plan

#### 7.2.1 Counterregulatory Responses during Insulin-induced Hypoglycemia

##### 7.2.1.1 Hormone Concentrations

Boxplots will be used to summarize the distribution of hormone levels separately for the two age groups by glucose level. An analysis of covariance model (ANCOVA) will be fit separately for each hormone with the change from baseline to peak during the subcutaneous insulin infusion test as the dependent variable. The model will include a term for age group (3-<7 vs. 12-<18) with baseline hormone concentration as the covariate.

A repeated measures regression model will also be fit treating each hormone measurement as a separate observation (instead of just using the peak value as above). Either an autoregressive or Toeplitz structure will be used to model the covariance pattern. Residual values will be checked for

918 approximate normality. If the distribution is highly skewed a transformation may be used.  
919 Suspected outliers will either be truncated or excluded.

920  
921 Additional exploratory models will be fit to assess possible associations of counterregulatory  
922 responses with the following covariates:

- 923 • age as continuous
- 924 • HbA1c
- 925 • gender
- 926 • BMI percentile
- 927 • clinical center
- 928 • glycemic indices as measured by the Guardian RT during home use prior to the  
929 subcutaneous insulin infusion test (see section 7.2.2.1)

930  
931 Continuous covariates will be modeled as linear in the dependent variable or divided into categories  
932 if significant non-linearity is detected. The number of hypoglycemic episodes per 24 hours  
933 measured by the Guardian RT will also be categorized as  $<2.0$  vs.  $2.0-<3.0$  vs.  $\geq 3.0$ .

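### For a non-linear baseline hormone, section 7.2.1.2 fixes categories as the remedy; a spline with the same degrees of freedom would leave less of any baseline difference in the adjusted age effect (minor)

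*Protocol*

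**What the plan says.** Protocol section 7.2.1.2 analyses, for each hormone, the glucose level at which a response is first seen. The model is parametric: "If the outcome values are not skewed a regression model with a normal distribution and interval" censoring, fitted by maximum likelihood. It has two independent variables: "Age group and the baseline hormone" value. The rule in question starts "If significant non-linearity is detected with the" and continues "baseline hormone, it will be divided into categories and treated as a discrete variable". The number of categories and the cut-points are not given. The alternative distributions named later in the section concern the outcome, not this covariate.

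The outcome is "treated as a secondary outcome" in 7.2.1.2, yet section 1.2 opens with "The primary objective of this study will be to compare the glucose level at which counter-regulatory" hormone responses occur. The model therefore addresses the question that the objectives put first. That mismatch of labels is a separate matter.

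Section 7.2.1.1 has a similar rule: "Continuous covariates will be modeled as linear in the dependent variable or divided into categories" when non-linearity is significant. It follows the list of covariates for the additional exploratory models.

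**The concern.** The two age groups are enrolled, not randomised, so their baseline hormone levels may differ, and baseline hormone is the only adjustment variable in the model. Cutting it into categories treats all children in a category as equal. If one age group has higher baselines overall, it will tend to have higher baselines inside each category too, and the age coefficient absorbs what is left. Three categories use 2 df. A restricted cubic spline with 3 knots also uses 2 df and keeps the full measurement. The plan thus names a remedy that adjusts less completely at the same price, in the comparison that section 1.2 calls primary.

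**Working it through.** **Inputs from the protocol.** 25 children per age group (2.1, 7.1). Interval-censored normal model with age group and baseline hormone (7.2.1.2). Samples when "glucose levels are <90, <80, <70, and <60 mg/dL" (3.3.2). Two-sided 5% test, epinephrine SD 306 pg/mL, difference 300 pg/mL, power about 92% (7.1).

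**The plan's own figure.** SE = 306 × √(2/25) = 86.5. Then 300/86.5 = 3.47, and Φ(3.47 − 1.96) = 93.4%. With the t distribution on 48 df the power is 92.5%. The stated 92% is reproduced. It concerns epinephrine, not trigger glucose, and this point does not change it.

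**Assumptions not in the protocol.** Normal baseline; age-group difference in baseline of 0, 0.5 or 1 SD; four non-linear shapes; trigger SD 10 mg/dL; baseline explaining 30% of within-group variance; true age effect zero.

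**Step 1: share of the baseline difference left after adjustment** (large sample, least squares). Share = age-effect bias after adjustment ÷ bias without adjustment. Example, exponential shape at 0.5 SD: tertiles 0.108/0.445 = 24%. Entries are for 0.5 SD / 1 SD.

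| Shape | Linear (1 df) | Median split (1 df) | Tertiles (2 df) | 3-knot spline (2 df) | Quartiles (3 df) | 4-knot spline (3 df) |
|---|---|---|---|---|---|---|
| S-shaped | 1 / 5% | 26 / 27% | 12 / 12% | 1 / 5% | 7 / 7% | 0 / 0% |
| Quadratic | 0 / 0% | 37 / 37% | 20 / 19% | 0 / 0% | 14 / 12% | 0 / 0% |
| Exponential | −1 / −3% | 40 / 40% | 24 / 23% | −1 / −3% | 17 / 15% | 0 / −1% |
| Plateau | 0 / 0% | 36 / 37% | 21 / 19% | 0 / 0% | 14 / 12% | 0 / 0% |

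In these shapes the linear term that the categories would replace also leaves little, at most 5% in size.

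**Step 2: the planned interval-censored model at N=50** (1,000 runs per setting; intervals cut at 58, 68, 78 and 88 mg/dL to mimic the first sample below each level). Bias of the age effect in mg/dL, for 0.5 SD / 1 SD:

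| Shape | Without adjustment | Tertiles | 3-knot spline | SD ratio, tertiles ÷ spline |
|---|---|---|---|---|
| S-shaped | 2.67 / 5.47 | 0.23 / 0.54 | −0.05 / 0.09 | 1.02 / 1.00 |
| Quadratic | 2.18 / 4.13 | 0.42 / 0.71 | 0.04 / −0.05 | 1.06 / 1.03 |
| Exponential | 2.44 / 4.64 | 0.49 / 1.03 | −0.10 / −0.10 | 1.05 / 1.04 |
| Plateau | 2.35 / 4.57 | 0.50 / 0.89 | 0.00 / −0.02 | 1.00 / 1.03 |

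The simulation error of a bias is about 2.4/√1000 to 2.9/√1000 = 0.08-0.09 mg/dL. The SD of the age estimate was 2.4-2.9 mg/dL, so tertile bias runs from 0.23/2.53 = 0.09 to 1.03/2.87 = 0.36 of it. With no age difference in baseline the bias was nil within simulation error and the SD ratio was 0.99-1.06. The worst variance ratio was (2.64/2.48)² = 1.13.

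**Step 3: the rule as written.** Categories apply only after a significant non-linearity test. The whole procedure was therefore simulated (linear unless significant, then tertiles or spline; least squares, log-normal baseline, R2 10-50%, N=50 and N=30). Wherever the age groups differed in baseline, the spline version had the smaller bias, by about 0.04-1.2 mg/dL. Its root mean squared error was equal within about 1%, or up to 11% lower.

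**The case against.** The strongest objection is that the fallback is conditional and the gain may disappear when it is used. In a separate interval-censored simulation (250 runs per setting, hence noisy), non-linearity was significant in 28-77% of trials at N=50 and 19-54% at N=30. Looking only at those trials, tertiles had the smaller absolute bias in 5 of 8 settings at R2 of 30%; the spline was better in all 8 at 50%. This stands as a limit on size. It does not overturn the point, because bias over the whole rule was still smaller with the spline.

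Other parts also stand:

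- The protocol gives no baseline hormone values, no age difference in them and no correlation with trigger glucose, so the size and direction of any bias are unknown.
- A baseline difference may itself be a consequence of age, and section 1.2 does not ask for an age effect net of baseline. The defensible statement is that the adjustment the plan has chosen is done less completely, not that a false age effect will be reported.
- A spline would not be better if the true relation stepped at the chosen cut-points.
- A log scale looks ideal when the simulated effect acts through log baseline. The protocol does not show that this is the right scale.

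The opening of chapter 7 says that a final analysis plan will supersede 7.2, so the number of categories and the cut-points can wait for it. But categorisation is a stated method, not a missing detail.

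**Conclusion.** The point holds as a minor one. If baseline hormone differs between the age groups, categories leave more of that difference in the adjusted age effect than a spline of equal df: 12-24% against at most 5% at 2 df, and 7-17% against at most 1% at 3 df. Over the conditional rule the excess is about 0 to 1.2 mg/dL for assumed baseline differences of 0.5-1 SD and R2 of 10-50%, which is below the standard error at N=50.

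Three stronger readings are tempting and are not supported:

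- A reader might infer that a fifth or more of a baseline difference will appear in the reported age effect. That presumes that categories are always used and that a baseline difference exists.
- A reader might infer a material loss of precision or power. The SD rises by about 0-6% in most settings, and the 92% in 7.1 belongs to another endpoint.
- A reader might infer that every continuous covariate in 7.2.1.1 is affected. The rule there sits under the exploratory models and does not clearly govern the baseline term of the ANCOVA.

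**What to change.** In 7.2.1.2, or in the analysis plan that will replace it, keep baseline hormone continuous. If non-linearity is detected, use a restricted cubic spline with 3 knots (2 df) and knot positions stated in advance, or a log transformation if baseline is skewed, instead of categories. Apply the same rule to the continuous covariates in the exploratory models of 7.2.1.1.

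The cost is a sentence of text and a line of code, with no more degrees of freedom than three categories and no extra subjects. The downside is that the covariate's own effect is shown as a curve instead of category means.

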### 949 **7.2.1.3 Hypoglycemic Symptoms**

951 Analysis of physiologic symptom measures from the HypoMon (if used) and symptom scores  
952 reported by the parent will parallel the methods described in section 7.2.1.1. If residual values from  
953 the regression models have a highly skewed distribution, then transformations will be explored. If  
954 no suitable transformation can be found for the parent-reported symptom scores, then ordinal  
955 logistic regression will be used instead.

## 956 **7.2.2 Continuous Glucose Monitor (CGM) Data**

### 958 **7.2.2.1 Glycemic Indices**

959 Analyses based on the Guardian RT will be based on 5 minute readings.

960  
961 Multiple sensor values  $<70$  mg/dL within 30 minutes will be considered a single hypoglycemic  
962 episode. Similarly, multiple values  $>200$  mg/dL within 30 minutes will be considered part of the  
963 same hyperglycemic episode.

964  
965 The following glycemic indices to be calculated for each subject:

- 966 • Mean glucose.

- 967 • Percentage of readings between 70-180 mg/dL.
- 968 • Hypoglycemia:
  - 969 ➤ Percentage of readings < 70, 60, 50 and 40 mg/dL.
  - 970 ➤ Area over the curve (a composite measure of percentage and severity of sensor
  - 971 values  $\leq 70$ mg/dL), defined as the area between the glucose curve and 70 mg/dL.
  - 972 ➤ Number of hypoglycemic episodes (as defined above) per 24 hours.
- 973 • Hyperglycemia:
  - 974 ➤ Percentage of readings > 180, 200, 250 and 300 mg/dL.
  - 975 ➤ Area under the curve (a composite measure of percentage and severity of sensor
  - 976 values >200mg/dL), defined as the area between 200 mg/dL and the glucose curve.
  - 977 ➤ Number of hyperglycemic episodes (as defined above) per 24 hours.

### 979 7.2.2.2 Accuracy

980 Laboratory glucose measurements will be used as the reference during the CRC Admission for  
 981 determination of the accuracy of the Guardian-RT. The subject's glucose meter (excluding values  
 982 used to calibrate the sensor) will be used as the reference during home use of the Guardian RT.  
 983 Sensor readings will be paired to reference values within  $\pm 2.5$  minutes. For each pair the following  
 984 difference measures will be calculated:

- 985 • Difference – Sensor minus reference value.
- 986 • Absolute Difference – Absolute value of the Difference.
- 987 • Relative Difference – Difference divided by the reference value.
- 988 • Relative Absolute Difference – Absolute value of the Relative Difference.
- 989 • ISO criteria – Sensor within  $\pm 15$  mg/dL if reference  $\leq 75$  mg/dL, or sensor within  $\pm 20\%$  if  
 990 reference >75 mg/dL).

991 Percentiles will be given for the four difference measures and the percentage of pairs meeting the  
 992 ISO criteria will be calculated. Results will be given separately for inpatient and outpatient data.  
 993 Values will be given overall and stratified by reference glucose, age group, gender, HbA1c and  
 994 BMI percentile. A Bland-Altman plot will be constructed. Confidence intervals and comparisons  
 995 of subgroups will use the bootstrap to account for correlated data from the same subject.  
 996

997  
 998 For each subject the glycemic excursion during the subcutaneous insulin infusion test will be  
 999 calculated separately for the reference and sensor values. This will be defined as the baseline minus  
 1000 the nadir glucose value. For the Guardian-RT, the nadir will be taken over the period from baseline  
 1001 to 60 minutes following completion of the subcutaneous insulin infusion test.

1002  
 1003 A scatterplot and Bland-Altman plot will be constructed to compare reference vs. CGM measured  
 1004 glucose drops during the subcutaneous insulin infusion test. Median values and quartiles will be  
 1005 given for each of the difference measures defined above. To investigate potential sensor lag, a  
 1006 scatterplot will be also constructed comparing the CGM vs. reference nadir times (defined as  
 1007 minutes from baseline). Summary statistics will be given for the difference of these two values.  
 1008

1009 A similar analysis will be done for the rise in glucose during the post-dinner blood draws described  
 1010 in section 4.2.

1011  
 1012 Sensitivity to detect hypoglycemia will be assessed by calculating the percentage of subjects with a  
 1013 sensor value <70, <60 and <50 mg/dL between baseline and 60 minutes following completion of the  
 1014 subcutaneous insulin infusion test. A similar sensitivity analysis for hyperglycemia will be done for  
 1015 those subjects with a reference glucose >200 mg/dL during the post-dinner blood draws.

1016  
1017 During home use of the Guardian RT, analysis of hypoglycemia detection will be based on clinical  
1018 events rather than individual points and will allow margins of error for both time (30 min) and  
1019 glucose (10 mg/dL). Multiple glucose values below the hypoglycemic threshold (e.g., <70 mg/dL)  
1020 within 30 minutes will be analyzed as a single event. Sensitivity will be defined as the percentage  
1021 of reference events for which the sensor alarmed within 30 minutes of the first low reference value.  
1022 The false positive rate will be defined as the percentage of sensor events for which all reference  
1023 values within 30 minutes of the first low sensor reading were above the hypoglycemic threshold.  
1024 Events where the sensor was always within  $\pm 10$  mg/dL of the reference, but on the opposite side of  
1025 the hypoglycemic threshold (e.g., sensor=68/reference=72) will not be counted as either a success  
1026 or a failure and will be excluded from the calculation. Parallel analyses will be conducted for  
1027 hyperglycemic episodes.  
1028  
1029

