### 235 **1.1.2 Evaluation of Continuous Glucose Monitoring Systems**

236 Real-time continuous glucose sensing systems offer the potential to markedly lower the risk of  
237 hypoglycemia in youth with T1DM. However, the DirecNet inpatient accuracy study demonstrated  
238 that the first generation of these devices was inaccurate when blood glucose was lowered to less  
239 than 70 mg/dl. In that study, children with T1DM between 3-17 years of age were admitted to the  
240 CRC for approximately 26 hours during which they wore 1-2 Medtronic MiniMed CGMS and 1-2  
241 Cygnus GlucoWatch G2 Biographer continuous glucose monitors. In every subject in that study,  
242 blood samples were obtained every 30-60 minutes from an indwelling intravenous catheter for  
243 measurement of reference plasma glucose levels in the DirecNet Central Laboratory. The Guardian-  
244 RT continuous glucose monitoring systems is a real-time continuous glucose monitor that has  
245 considerable promise for use in children with diabetes. Therefore, a secondary aim of this study is  
246 to obtain very important data regarding the accuracy of this system during hypoglycemia in young  
247 children, as well as adolescents.

248

249 The Guardian-RT has been approved by the FDA for detecting trends and tracking patterns in adults  
250 (18 and older) and are indicated for adjunctive rather than replacement of standard home glucose  
251 monitoring devices. The sensor has been approved by the FDA for use for up to 72 hours but can  
252 function for a longer period of time.

253

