  - 566 ○ If the sensor is not functioning at the time of the admission, a new sensor will be  
567 inserted.
- 568 • For subjects of sufficient size, a second Guardian-RT will be inserted. The time of  
569 placement and the placement site of each sensor will be recorded.  
570

571  
572 For subjects of sufficient weight to accommodate the blood volume requirements, reference glucose  
573 measurements will be made every 30 minutes during the CRC admission for evaluation of the  
574 accuracy of the Guardian-RT. The blood draws will be timed to be on the half-hour.  
575

576 During the insulin-induced hypoglycemia test, blood glucose measurements will be made as  
577 described in section 3.3.  
578

579 For subjects of appropriate weight to accommodate the volume of blood required for testing, the  
580 Guardian RT will be assessed following a physiologic rise in blood glucose after dinner.  
581

582 Before starting the post-meal glucose measurements, a blood glucose level will be obtained using  
583 the study HGM. The subject's usual meal dose (the dose for the carbohydrates to be  
584 consumed) will be given, and a correction dose will be given if needed. Reference glucose levels  
585 will be obtained at baseline (when the subject finishes the meal) and every 15 minutes for 120  
586 minutes.  
587

588 **4.2.1 Volume of Blood Draws**

589 Each blood draw will require a blood volume of approximately 1.3 ml per blood draw at the  
590 "discard" centers and 0.3 ml per blood draw at the "reinfusion" centers. At the "discard" centers,  
591 the maximum number of blood draws based on the subject's weight will be calculated at the time of  
592 admission so that the maximum blood volume drawn will not exceed 5% (at reinfusion centers, the  
593 maximum blood volume drawn will not approach 5%). Section 5.5.6 provides further details on the  
594 blood volume requirements.  
595

596 **4.2.2 Quality Control Specimens**

597 Approximately 5% of the reference blood samples collected for evaluation of the Guardian-RT will  
598 be collected in duplicate to send to the central lab for quality control purposes.  
599

600 **4.2.3 Sensor Considerations during Inpatient CRC Admission**

601 **4.2.3.1 Sensor Calibrations**

602 If a calibration of the Guardian-RT is required during the admission, it will be performed by  
603 study/CRC personnel using a fingerstick sample.

604

605 **4.2.3.2 Sensor Failure**

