789 blood draws is then determined by dividing this maximum blood volume by the amount of blood in  
790 each blood draw at the center.

791

792 The table below shows the blood volumes for each procedure at the "reinfusion" and "discard"  
793 centers. For blood draws for evaluation of the accuracy of the Guardian RT a blood volume of 1.3  
794 ml per blood draw at the "discard" centers and 0.3 ml per blood draw at the "reinfusion" centers is  
795 assumed. At the "discard" centers, the maximum number of blood draws per subject will be  
796 adjusted if the blood draw amount exceeds 1.3 ml.

797

798 **Table 5.1 Blood Volume Requirements for Procedures According to Type of Blood Draw**

Procedure	# of blood draws	Type of Blood Draw Employed at the Clinical Center	
		"Reinfusion" (Volume to be drawn)	"Discard" (Volume to be drawn)
A. Subcutaneous Insulin Infusion Test	6	44.5 (0.3 ml per blood draw)	60.5 (1.3 ml per blood draw)
B. Half-Hourly measurements for 12 hrs	24	7.2	31.2
C. Quality control sample	1	0.3	1.3
D. Meal-induced hyperglycemia test	8	2.4	10.4

799

800 The tables below indicate the procedures to be done based on the age and/or weight of the subjects.

801  
802 **Table 5.2: Procedures to Be Done / Blood Volume Required According to Weight of Subject**

803  
804 **A. “Reinfusion” Centers**

	Procedure (see description in Table 5.1 for each ‘letter’)				
Subject Weight	A	B	C	D	Total Blood Volume
12.8 to <14.9 kg	44.5	--	0.3	--	44.8
14.9 to 15.5 kg	44.5	7.2	0.3	--	52.0
>15.6 kg	44.5	7.2	0.3	2.4	54.4

805

806

807 **B. “Discard” Centers**

	Procedure (see description in Table 5.1 for each ‘letter’)				
Subject Weight	A	B	C	D	Total Blood Volume
17.4 to <26.3 kg	60.5	--	0.3	-	60.8
26.3 to 29.2 kg	60.5	31.2	0.3	-	92.0
>29.3 kg	60.5	31.2	0.3	10.4	102.4

808

\* based on adjusted schedule of every 30 min overnight (9PM – 6AM) and hourly at other times

809

810 The study may include other risks that are unknown at this time.

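### Weight cut-offs give light young children only insulin-test reference draws, so the pooled inpatient age-group accuracy figures mix age with glucose conditions

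*Protocol*

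**What the plan says.** Section 7.2.2.2 plans percentiles of four difference measures and the percentage of pairs meeting the ISO criteria, with inpatient and outpatient data kept apart. On strata it says: "Values will be given overall and stratified by reference glucose, age group, gender, HbA1c and" BMI percentile. Subgroup comparisons use the bootstrap, to allow for correlation within a subject. The section states no crossing of age group with reference glucose or with the type of draw, and no restriction to a set of draws common to all subjects.

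Section 4.2 makes the half-hourly reference draws conditional on weight ("For subjects of sufficient weight to accommodate the blood volume requirements, reference glucose" measurements every 30 minutes) and does the same for the post-dinner draws. Tables 5.1 and 5.2 in section 5.5.6 give the detail:

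- "A. Subcutaneous Insulin Infusion Test": 6 draws, at every eligible weight.
- "B. Half-Hourly measurements for 12 hrs": 24 draws, from 14.9 kg at reinfusion centers and 26.3 kg at discard centers.
- "D. Meal-induced hyperglycemia test": 8 draws, from about 15.6 kg (reinfusion) and 29.3 kg (discard).

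The lowest reinfusion band, "12.8 to <14.9 kg", and the lowest discard band, 17.4 to <26.3 kg, have the insulin test and one quality-control sample only. The discard band "26.3 to 29.2 kg" adds the half-hourly draws but not the meal draws.

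Section 1.1.2 gives the secondary aim: "to obtain very important data regarding the accuracy of this system during hypoglycemia in young" children, as well as adolescents.

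**The concern.** The age groups are 3.0 to 7.0 and 12.0 to <18.0 years, so a weight rule is close to an age rule. The restriction falls on the young group, and a restricted child supplies pairs only from a test in which glucose is driven down. Section 1.1.2 itself reports that first-generation sensors were inaccurate below 70 mg/dL. If this sensor is also less accurate there, a pooled young stratum with a larger share of insulin-test pairs will look worse than a pooled adolescent stratum for that reason alone. The bootstrap corrects the interval for clustering. It does not remove a difference in the mix of conditions. A difference in sampling could then be read as worse sensor performance in young children.

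**Working it through.** **1. The plan's cut-offs.** Section 5.5.6 allows 5% of 70 ml/kg, which is 3.5 ml/kg. Minimum weight = total volume / 3.5.

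| Center type | Procedures | Volume (ml) | Volume / 3.5 (kg) | Stated (kg) |
|---|---|---|---|---|
| Reinfusion | A, C | 44.8 | 12.80 | 12.8 |
| Reinfusion | A, B, C | 52.0 | 14.86 | 14.9 |
| Reinfusion | A, B, C, D | 54.4 | 15.54 | 15.6 |
| Discard | A, C | 60.8 | 17.37 | 17.4 |
| Discard | A, B, C | 92.0 | 26.29 | 26.3 |
| Discard | A, B, C, D | 102.4 | 29.26 | 29.3 |

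All six reproduce when rounded up to the next 0.1 kg.

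**2. Mix per subject** (one sensor, quality-control duplicate left out).
- Restricted child: 6/6 = 100% insulin-test draws.
- Full schedule: 6 + 24 + 8 = 38 draws; insulin test 6/38 = 16%; half-hourly and meal 32/38 = 84%. That 84% becomes 71-90% if the insulin test is counted as 5 to 13 draws and the half-hourly series as 24 to 36.

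**3. Mix per age stratum.** Let f be the fraction of young children restricted, with the rest on the full schedule. Mean draws per young child = 6f + 38(1 - f) = 38 - 32f. Insulin-test share of the young stratum = 6/(38 - 32f). It reaches one half when 38 - 32f = 12, so f = 26/32 = 0.81.

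**4. Illustrative false gap.** Assumptions, none from the protocol:
- the sensor is identical in both ages;
- relative error is normal with mean zero, SD 20% at higher glucose and 30-45% at low glucose;
- the low pairs are the three insulin-test draws triggered at <80, <70 and <60 mg/dL, and no half-hourly or meal pair is low;
- every adolescent is on the full schedule.

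The low share is 3/(38 - 32f) in the young stratum and 3/38 = 8% in adolescents. The median absolute relative error x solves (1 - p)[2Φ(x/0.20) - 1] + p[2Φ(x/s) - 1] = 0.5, where p is the low share and s is 0.30 or 0.45. For adolescents x is 13.9% (s = 0.30) or 14.2% (s = 0.45).

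| f | Insulin-test share, young | Low share, young | False gap (points) |
|---|---|---|---|
| 0.2 | 19% | 9% | 0.1-0.15 |
| 0.5 | 27% | 14% | 0.3-0.55 |
| 0.8 | 48% | 24% | 0.9-1.7 |
| 0.9 | 65% | 33% | 1.4-2.7 |
| 1.0 | 100% | 50% | 2.5-5.2 |

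**5. Weight of each age in the overall figure.** With equal group sizes, adolescents supply 38/(76 - 32f) of inpatient pairs: 63% at f = 0.5 and 75% at f = 0.8.

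**The case against.** The strongest reply concerns size. A reader might infer that the young stratum as a whole consists mainly of falling and low glucose, or that a gap of 2.5-5 points is to be expected. The protocol supports neither. A full-schedule child gives more than six times as many pairs as a restricted one, so at f = 0.5 some 73% of young pairs are still half-hourly or post-meal. The protocol gives neither expected weights nor the number of discard centers among the five. At reinfusion centers only the band up to 14.9 kg is fully restricted, so a large f would have to come from discard centers. A reader might also set the gap against the ±1.0% in section 7.1. That precision is for all 1,800-3,000 pairs pooled and rests on a pilot of another sensor, so it is no yardstick for an age contrast. All of this stands, and it limits the size of the problem.

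Other analyses also help. The glucose-drop, nadir-timing and hypoglycemia-sensitivity analyses use the insulin test, which every subject has. Results by reference glucose are planned, and post-dinner data have their own analysis. The accuracy objective in section 1.2 names no age contrast, and Chapter 7 calls section 7.2 a framework that the final analysis plan will supersede. These points soften the concern without removing it. None of those analyses is specified by age group. Section 7.2.2.2 does plan age strata and subgroup comparisons on inpatient pairs, and the protocol itself fixes the unequal sampling.

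**Conclusion.** The concern holds as a matter of comparability, with a size that the protocol leaves open. Table 5.2 and section 7.2.2.2, followed as written, give an inpatient age comparison confounded with glucose conditions. A sensor less accurate at low glucose would look worse in young children even with identical performance at each glucose level. Under the assumed error model the false gap is small at moderate f (0.3-0.55 points at f = 0.5), grows to 0.9-1.7 at f = 0.8, and reaches 2.5-5.2 only if every young child is restricted. The conclusion rests on three assumptions: nearly all adolescents are on the full schedule, accuracy is worse at low glucose, and young children who are not restricted have all procedures. Home results use meter references that do not depend on the weight bands, and are not affected. The point is worth settling before the data are seen. It concerns a secondary analysis and does not touch the hormone comparison.

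**What to change.** In section 7.2.2.2, or in the analysis plan that replaces it, base the inpatient age-group comparison on the insulin-test draws that every subject has, within reference-glucose bands. Report half-hourly and post-meal pairs in separate tables, with the numbers of subjects and pairs per age group. If a pooled age-stratified figure is kept, label it descriptive and not comparable between ages.

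This takes a few sentences and some additional tables, and no new data. The price is fewer pairs and wider bootstrap intervals for the age comparison: on the Table 5.1 count, 6 insulin-test draws per subject per sensor in place of up to 38.
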